TITLE Assessment of the Impact of Real-time Continuous Glucose Monitoring on People Presenting with Severe Hypoglycaemia

DESIGN Randomised open-label parallel group study

AIMS This study aims to assess the impact of real-time continuous glucose monitoring on the frequency, duration, awareness and severity of hypoglycaemia in people with type 1 diabetes and a recent history of severe hypoglycaemia, compared to usual care.

OUTCOME MEASURES The primary outcome is % time spent in hypoglycaemia (<3.0mmol/L, 55mg/dL). Secondary outcomes include other measures of hypoglycaemia, time in euglycaemia, overall glucose status and patient reported qualitative measures.

POPULATION Adults with type 1 diabetes, who are CGM naïve, and having a recent episode of severe hypoglycaemia (<72hrs).

ELIGIBILITY Participants with type 1 diabetes and severe hypoglycaemia requiring ambulance call-out or emergency department attendance within 72 hours.

DURATION 12 weeks for each participant, 52 weeks in total.

1. INTRODUCTION

1.1 BACKGROUND

Type 1 diabetes (T1DM), which affects 300,000 in the UK, is characterised by autoimmune destruction of the pancreatic beta cells, leading to absolute deficiency of insulin. Management of T1DM requires exogenous insulin administration, aiming for glucose concentrations as close to physiological values as possible. Intensive management of T1DM improves glucose control and reduces the risk of microvascular diabetes complications and cardiovascular disease [1]. In the UK diabetes consumes more than 10% of the National Health Service budget [2] and in the USA a relatively greater amount is spent on type 1 compared with type 2 diabetes (8.6% of the diabetes budget compared with 5.6% of diabetes prevalence) [3]. Medication and insulin pump therapy accounts for less than 10% of diabetes expenditure with the majority of costs incurred in the treatment of complications [4].

Optimal control remains challenging to achieve and intensive insulin treatment increases the risk of severe hypoglycaemia, with lower glucose values also associated with an increased frequency and severity of moderate hypoglycaemia [5, 6]. Severe hypoglycaemia is defined as any episode of hypoglycaemia requiring the assistance of a third party actively to treat. Hypoglycaemia is associated with morbidity and even mortality, and places a financial burden on health systems.

Severe hypoglycaemia costs £13million per year in NHS costs [7]. Between 4 and 10% of deaths in people with type 1 diabetes are attributed to hypoglycaemia and the risk of severe hypoglycaemia increases 6-fold in people with impaired awareness of hypoglycaemia. Avoidance of hypoglycaemia is associated with restoration of hypoglycaemia awareness and this may be enabled by the use of continuous glucose monitoring.

In type 1 diabetes real-time continuous glucose monitoring (CGM) improves overall glucose control in all age groups when used continuously, reduces hypoglycaemia in people with an HbA1c <7.0%, and may reduce severe hypoglycaemia [8-10].

In England continuous glucose monitoring is supported by NICE for people with type 1 diabetes who are willing to commit to using it at least 70% of the time and to calibrate it as needed, and who have any of the following despite optimised use of insulin therapy and conventional blood glucose monitoring [11]:

- More than 1 episode a year of severe hypoglycaemia with no obvious preventable precipitating cause.
- Complete loss of awareness of hypoglycaemia.
- Frequent (more than 2 episodes a week) asymptomatic hypoglycaemia that is causing problems with daily activities.
- Extreme fear of hypoglycaemia.
- Hyperglycaemia (HbA1c level of 75 mmol/mol [9%] or higher) that persists despite testing at least 10 times a day

Addressing severe hypoglycaemia, reducing the risk of further episodes and acting promptly to optimise hypoglycaemia awareness are critical in people at high risk.

1.2 RATIONALE FOR CURRENT STUDY

This clinical study proposes to assess the impact of real-time continuous glucose monitoring supported remotely by a specialist healthcare team on the frequency, duration, awareness and severity of hypoglycaemia in people with type 1 diabetes and a recent history of severe hypoglycaemia.

1.3 HYPOTHESIS

Real-time CGM with adjunctive healthcare professional support provided within 72 hours of an episode of severe hypoglycaemia has a beneficial impact on hypoglycaemia frequency, duration, severity and awareness in those at highest risk of significant morbidity and mortality, compared with self-monitoring of blood glucose with adjunctive support.

2. STUDY OBJECTIVES

Primary outcome: % time spent in hypoglycaemia (<3.0mmol/L, 55mg/dL)

Secondary outcome: Number of episode of serious hypoglycaemia (defined as a sensor glucose <3.0mmol/L (55mg/dL) for >20 minutes)

% time spent in hypoglycaemia (<3.9mmol/L, 70mg/dL)

% time in euglycaemia (3.9-7.8mmol/L, 70-140mg/dL)

% time spent in target (3.9-10mmol/L, 70-180mg/dL)

% time spent in hyperglycaemia (>10mmol/L, 180mg/dL)

Number hypoglycaemic excursions

Severe hypoglycaemia

MAD%

Glucose variability

HbA1c

Ambulance call-out rates

Diabetes treatment satisfaction questionnaire

CGM usability

PAID

Gold score

Fear of hypoglycaemia survey score (HFS2)

Cost effectiveness

3. STUDY DESIGN

Randomised controlled study comparing the impact of real-time CGM with usual care following severe hypoglycaemia (Figure 1).

[figure not shown]

Figure 1. Study design

3.1 RECRUITMENT

Recruitment will be undertaken in collaboration with the London Ambulance Service and from the Accident and Emergency departments of St Marys Hospital and Charing Cross Hospital in London (recruitment flow chart below). Participants will be identified following an episode of severe hypoglycaemia and participant information sheets will be given to potential subjects. Following any questions, London Ambulance Services and Emergency Departments will seek verbal consent to share details with study investigators, and send details to principal investigator through a secure website (NHS.net account).

[figure not shown]

Figure 2. Recruitment Flow Chart

3.2 FEASIBILITY

London Ambulance Service call outs for hypoglycaemia in selected geographical areas of North West London in 2015 calendar year are as follows:

Region	Number of call outs	Conveyed to emergency department
NWL London (Harrow)	286	160
Hillingdon	468	321
Brent	499	335
North Central	311	174
Hounslow	343	210
Hammersmith/ Fulham	245	167
TOTAL	2152	1367

Between 1st March 2014 and 28th February 2015, 236 people attended the emergency departments of Imperial College Healthcare NHS Trust with a coded diagnosis of hypoglycaemia.

3.3 STUDY DURATION

12 weeks for each participant, 52 weeks in total.

4. PARTICIPANT ENTRY

4.1 PRE-REGISTRATION EVALUATIONS

Episode of severe hypoglycaemia

Age >18 years

Diagnosis of type 1 diabetes

4.2 INCLUSION CRITERIA

Adults over 18 years of age

Severe hypoglycaemia requiring ambulance call-out or emergency department attendance within 72 hours

Type 1 diabetes confirmed on the basis of clinical features

Type 1 diabetes for greater than 3 years

4.3 EXCLUSION CRITERIA

Use of CGM or Abbott Freestyle Libre device within the last 6 months (except short periods of diagnostic blinded use under clinic supervision)

Use of pre-mixed insulin

Use of regular paracetamol

No access to smartphone or computer

Pregnant or planning pregnancy

Breastfeeding

Have active malignancy or under investigation for malignancy

Severe visual impairment

Reduced manual dexterity

Unable to participate due to other factors, as assessed by the Chief Investigators

4.4 WITHDRAWAL CRITERIA

Participants will be withdrawn if their ability to give informed consent is impaired. Participants will also be withdrawn, at the chief investigators discretion, if glucose control is negatively impacted by the use of either intervention.

5. ADVERSE EVENTS

5.1 DEFINITIONS

Adverse Event (AE): any untoward medical occurrence in a patient or clinical study subject.

Serious Adverse Event (SAE): any untoward and unexpected medical occurrence or effect that:

- **Results in death**
- **Is life-threatening** – refers to an event in which the subject was at risk of death at the time of the event; it does not refer to an event which hypothetically might have caused death if it were more severe
- **Requires hospitalisation, or prolongation of existing inpatients' hospitalisation**
- **Results in persistent or significant disability or incapacity**
- **Is a congenital anomaly or birth defect**

Medical judgement should be exercised in deciding whether an AE is serious in other situations. Important AEs that are not immediately life-threatening or do not result in death or hospitalisation but may jeopardise the subject or may require intervention to prevent one of the other outcomes listed in the definition above, should also be considered serious.

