5.3 REPORTING PROCEDURES

All adverse events should be reported. Depending on the nature of the event the reporting procedures below should be followed. Any questions concerning adverse event reporting should be directed to the Chief Investigator in the first instance.

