5.3.1 Non serious AEs

All such events, whether expected or not, should be recorded.

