5.3.2 Serious AEs

An SAE form should be completed and faxed to the Chief Investigator within 24 hours. However, hospitalisations for elective treatment of a pre-existing condition do not need reporting as SAEs.

All SAEs should be reported to the NRES Committee **xxx** where in the opinion of the Chief Investigator, the event was:

- 'related', i.e. resulted from the administration of any of the research procedures; and
- 'unexpected', i.e. an event that is not listed in the protocol as an expected occurrence

Reports of related and unexpected SAEs should be submitted within 15 days of the Chief Investigator becoming aware of the event, using the NRES SAE form for non-IMP studies. The Chief Investigator must also notify the Sponsor of all SAEs.

Local investigators should report any SAEs as required by their Local Research Ethics Committee, Sponsor and/or Research & Development Office.

Contact details for reporting SAEs
[contact], attention [name]
Please send SAE forms to:
Diabetes, Endocrinology and Metabolism Medicine
Imperial College
[name]
St Mary's Campus
[name]
[name]
[contact] (Mon to Fri 09.00 – 17.00)

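### Section 5.1 builds expectedness into the SAE definition and section 5.3.2 uses it again as a filter, so the expedited reporting duty for a hospitalised recurrence of severe hypoglycaemia is inconsistent

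*Combined protocol and SAP*

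**What the plan says.** Section 5.1 defines an adverse event with no reference to expectedness. It then defines an SAE as "any untoward and unexpected medical occurrence or effect that" leads to one of five outcomes: death, threat to life, new or prolonged hospitalisation, lasting disability, or birth defect. It does not say what unexpected means. A further paragraph allows medical judgement in other situations: important events that fall short of death or hospitalisation but may lead to one of the "outcomes listed in the definition above, should also be considered serious".

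Section 5.3 opens with a general rule: "All adverse events should be reported". The route then depends on the type of event:

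- Section 5.3.1, on non-serious events: "All such events, whether expected or not, should be recorded".
- Section 5.3.2, on SAEs: "An SAE form should be completed and faxed to the Chief Investigator within 24 hours", and "The Chief Investigator must also notify the Sponsor of all SAEs". Neither sentence has an expectedness test. The one stated exemption is that "hospitalisations for elective treatment of a pre-existing condition do not need reporting as SAEs".
- Section 5.3.2 also sends an SAE to the ethics committee when it is both related to the research procedures and unexpected. Here unexpected is explained as "an event that is not listed in the protocol as an expected occurrence".

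The protocol text contains no list of expected occurrences.

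**The concern.** Seriousness and expectedness are separate properties. Section 5.3.2 treats them so: it starts from all SAEs and picks out the unexpected ones for the committee. Section 5.1 merges them, so that, read literally, an expected event cannot be an SAE however grave its outcome.

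This matters more here than in most trials. Participants enter because of an episode of severe hypoglycaemia within the previous 72 hours (section 4.2), and severe hypoglycaemia and ambulance call-outs are secondary outcomes (section 2). Recurrence is the serious event that anyone running the study would foresee. If foreseeable means expected, that event is the first to drop out of the SAE definition.

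What is at stake is SAE classification, the 24-hour form to the Chief Investigator, the notice to the sponsor, and any count of SAEs by arm built on the definition. Two members of staff could classify the same admission differently and each point to the protocol in support.

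**Working it through.** No figure in the plan needs to be reproduced. The check traces one event, an emergency admission for recurrent severe hypoglycaemia, through sections 5.1 to 5.3.2 under each meaning of unexpected.

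| Reading | Meets the listed SAE definition in 5.1? | 24-hour form and sponsor notice? |
|---|---|---|
| (a) Ordinary meaning: not foreseeable | No. The event is foreseeable in this population | Not triggered |
| (b) Meaning in 5.3.2: not listed as expected | Yes. No event is listed, so it counts as unexpected, and it involves hospitalisation | Required |
| (c) Structure of 5.3.2: expectedness matters only for the committee report | Yes, through hospitalisation alone | Required |

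Reading (a) gives a different duty from (b) and (c). Four further points bear on it.

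1. *Where the event goes under (a).* The only other stated route is 5.3.1, which covers expected events but asks only that they be recorded.
2. *Medical judgement.* That paragraph of 5.1 addresses events that do not result in death or hospitalisation, so it does not clearly bring back an expected admission. It also has no expectedness test. Under (a), a lesser event could therefore be serious although expected, while an admission would not qualify under the list.
3. *The elective exemption.* A planned admission is expected in the ordinary sense. If 5.1 already excluded expected events, the exemption in 5.3.2 would be largely redundant.
4. *The committee filter.* It selects unexpected SAEs from all SAEs. Under 5.1 as worded, all SAEs are already unexpected and that half of the filter does nothing.

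Points 2 to 4 suggest that the word in 5.1 is loose drafting. They do not remove it.

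**Size.** The documents give no recurrence or admission rate. Section 3.2 reports 1367 of 2152 ambulance call-outs conveyed to an emergency department (1367/2152 = 63.5%), but conveyance is not admission and the figures are not confined to type 1 diabetes. The risks below are therefore assumptions; only the 55 participants (section 7) come from the documents. Events affected = assumed 12-week risk × 55, taking one hospitalised recurrence per affected participant:

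- 2%: 0.02 × 55 = 1.1
- 5%: 0.05 × 55 = 2.75, about 2.8
- 10%: 0.10 × 55 = 5.5
- 20%: 0.20 × 55 = 11.0

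Under (a) none of these would meet the listed definition; under (b) or (c) all would.

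**The case against.** The strongest reply is that the protocol defines unexpected once, in 5.3.2, and that this meaning should be carried back to 5.1. Since nothing is listed as expected, a hospitalised recurrence is then an SAE and the form and notice are due. This is a fair reading and probably close to the intent, but it does not settle the matter. Section 5.1 does not refer to the later definition. The reading also works only while no list exists: if the protocol were amended to list recurrent severe hypoglycaemia as expected, as the committee filter invites, the event would leave the committee report and, through 5.1, the listed SAE definition as well.

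A second reply is that 5.3.1 is headed for non-serious events, and an admission for severe hypoglycaemia is not plainly one of those. That is right as far as it goes: under (a) the event has no clean route. It still does not acquire the 24-hour form or the sponsor notice.

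Third, all adverse events must be reported, and section 5.3 directs queries to the Chief Investigator. These are real backstops, and they limit the harm. They set no 24-hour limit, and someone who has classed an event as non-serious has no reason to ask.

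Fourth, the range of 1 to 11 events rests on assumed risks. That stands. The range shows scale only, and the inconsistency does not depend on it.

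**Conclusion.** The concern holds. Section 5.1 makes expectedness a condition of being an SAE, while 5.3.2 presupposes that expected SAEs exist and attaches the form and the sponsor notice to SAEs without any such condition. Read literally, 5.1 takes the most foreseeable serious event in this population out of expedited reporting. Read with the meaning in 5.3.2, it keeps that event in.

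The consequence is limited to SAE classification, expedited reporting and SAE counts. The event is still reported as an adverse event, and severe hypoglycaemia and ambulance call-outs are collected as outcomes. The planned efficacy comparisons, sample size and power are untouched. The number of events affected cannot be derived from the documents; about 1 to 11 is an illustration under assumed risks of 2% to 20%. The wording should be corrected, but it does not threaten the validity of the trial.

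**What to change.** Delete the words *and unexpected* from the SAE definition in section 5.1, so that seriousness rests on the five listed outcomes and the medical-judgement paragraph alone. Keep expectedness only in section 5.3.2, as the filter for reports to the ethics committee.

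In the same amendment it would help to state which occurrences, if any, count as expected. With none listed, the expectedness half of the filter excludes nothing, and every related SAE goes to the committee. Once 5.1 is corrected, such a list would affect only the committee report and not the form or the sponsor notice.

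The cost is a wording amendment and a few more SAE forms, about 1 to 11 under the assumed range. No treatment, visit or analysis changes.

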5.3 REPORTING PROCEDURES

All adverse events should be reported. Depending on the nature of the event the reporting procedures below should be followed. Any questions concerning adverse event reporting should be directed to the Chief Investigator in the first instance.

5.3.1 Non serious AEs

All such events, whether expected or not, should be recorded.

5.3.2 Serious AEs

An SAE form should be completed and faxed to the Chief Investigator within 24 hours. However, hospitalisations for elective treatment of a pre-existing condition do not need reporting as SAEs.

All SAEs should be reported to the NRES Committee **xxx** where in the opinion of the Chief Investigator, the event was:

- 'related', i.e. resulted from the administration of any of the research procedures; and
- 'unexpected', i.e. an event that is not listed in the protocol as an expected occurrence

Reports of related and unexpected SAEs should be submitted within 15 days of the Chief Investigator becoming aware of the event, using the NRES SAE form for non-IMP studies. The Chief Investigator must also notify the Sponsor of all SAEs.

Local investigators should report any SAEs as required by their Local Research Ethics Committee, Sponsor and/or Research & Development Office.

Contact details for reporting SAEs
[contact], attention [name]
Please send SAE forms to:
Diabetes, Endocrinology and Metabolism Medicine
Imperial College
[name]
St Mary's Campus
[name]
[name]
[contact] (Mon to Fri 09.00 – 17.00)

6. ASSESSMENT AND FOLLOW-UP

6.1 CLINIC VISIT 1: Screening and Randomisation

Following informed consent study participants will give a full medical and medication history, as well as undergo a physical examination and ECG. Venous blood tests will be taken and sent to assess HbA1c, plasma glucose, renal function, serum C-peptide, thyroid function test, 9 am cortisol and coeliac screen (tissue transglutaminase antibody). Women of childbearing age will have a urine pregnancy test. If participants meet the inclusion criteria they will be enrolled on to the study and will complete a semi-structured participant interview and questionnaires (Diabetes treatment satisfaction questionnaire, CGM usability, PAID, and Fear of hypoglycaemia survey score (HFS2)). A Gold Score questionnaire will also be completed.

Participants enrolled will be randomised to real-time continuous glucose monitoring (RT CGM) or self-monitoring blood glucose (SMBG) group. Randomisation will be done using sealedenvelope.com and stratified by insulin delivery modality.

The RT CGM group will receive a Dexcom G6 transmitter and sensors, as well as a structured education refresher focusing on hypoglycaemia avoidance, recognition, and management. Participants in the SMBG group will receive the same structured education refresher focusing on hypoglycaemia avoidance, recognition, and management. All education will be delivered by the research nurse from a predefined curriculum and will be supported by independent written materials.

Participants will be instructed to test their capillary blood glucose if symptoms of hypo- or hyperglycaemia occur, in case of sensor failure or if the sensor glucose is out of the desired range. Participants using the G6 sensor will change sensor every ten days (or sooner in the event of sensor failure). Low glucose alert settings will be standardised at 4.4 mmol/L (80mg/dL) for all participants at the start of the study and can be reduced to 4 mmol/L (70mg/dL) at week 2 during the telephone visit depending on participant preference. High glucose alerts may be personalised.

The SMBG group will additionally undergo blinded CGM at weeks 1 and 2, weeks 4 to 6 and weeks 9 to 12 using the Dexcom G6 system. Participants in this group will be shown how to insert the Dexcom G6 at the first clinic visit and sensors provided so they can do this at home.

6.2 FOLLOW-UP: Telephone follow-up during study period

Participants will be provided telephone support twice in the first week, then weekly for the next 3 weeks, and every 2 weeks thereafter, to optimise glucose and reduce the risk of further hypoglycaemia.

Participants in the CGM group with an iOS or Android smartphone will be able to upload and share data with the Research team through the “Dexcom Share app”. Participants who do not have a smartphone can upload their CGM data to an online platform named “Tidepool” using a PC or Mac desktop computer. In total, participants will use CGM for 12 weeks.

Participants in the SMBG group will be asked to self-monitor a minimum of 4 times daily and upload data to Tidepool, an online not-for-profit platform for individuals to selectively share data with clinicians to optimise diabetes management. They will receive telephone support from the research team, based on their Tidepool data, at the same time points as the RT-CGM group to optimise glucose and reduce the risk of further hypoglycaemia. Blinded CGM data from the SMBG group will be uploaded at the end of week 2, end of week 6 and end of week 12.

6.3 CLINIC VISIT 2: End of study

At the end of the study (i.e. at end of 12 weeks), repeat blood tests to assess HbA1c will be performed. Participants will be asked to complete questionnaires and a semi-structured interview will be conducted, similar to that at baseline. Participants will return study equipment and return to their standard care.

